Appendix 2. Investigator’s Global Assessment (IGA)

A subject is said to have achieved the IGA response when all the following are true:

- IGA score is 0 (clear) or 1 (almost clear)
- IGA score improvement ≥ 2

Appendix 3. Eczema Area and Severity Index (EASI)

The EASI quantifies the severity of a subject’s atopic dermatitis based on both severity of lesion clinical signs and the percent of BSA affected. EASI is a composite scoring by the atopic dermatitis clinical evaluator of the degree of erythema, induration/papulation, excoriation, and lichenification (each scored separately) for each of four body regions, with adjustment for the percent of BSA involved for each body region and for the proportion of the body region to the whole body. Lesion Severity by Clinical Signs: The basic characteristics of atopic dermatitis lesions - erythema, induration/papulation, excoriation, and lichenification - provide a means for assessing the severity of lesions. Assessment of these four main clinical signs is performed separately for four body regions: head and neck, upper limbs, trunk (including axillae and groin) and lower limbs (including buttocks). Average erythema, induration/papulation, excoriation, and lichenification are scored for each body region according to a 4 point scale: 0 = absent; 1 = mild; 2 = moderate; 3 = severe. Morphologic descriptors for each clinical sign severity score are shown in Table 4.

Table 4. Clinical Sign Severity Scoring Criteria for the Eczema Area and Severity Index (EASI)

Score		Description*
Erythema (E)		
0	Absent	None; may have residual discoloration (post-inflammatory hyperpigmentation and/or hypopigmentation).
1	Mild	Light pink to light red
2	Moderate	Red
3	Severe	Deep, dark red
Induration/Papulation (I)		
0	Absent	None
1	Mild	Barely palpable to slight, but definite hard thickened skin and/or papules
2	Moderate	Easily palpable moderate hard thickened skin and/or papules
3	Severe	Severe hard thickened skin and/or papules
Excoriation (Ex)		
0	Absent	None
1	Mild	Slight, but definite linear or picked scratch marks or penetrating surface injury
2	Moderate	Moderate linear or picked scratch marks or penetrating surface injury
3	Severe	Severe linear or picked scratch marks or penetrating surface injury
Lichenification (L)		
0	Absent	None
1	Mild	Barely perceptible to slight, but definite thickened skin, fine skin markings, and lichenoid scale
2	Moderate	Moderate thickened skin, coarse skin markings, and coarse lichenoid scale
3	Severe	Severe thickened skin with very coarse skin markings and lichenoid scale

* The EASI will exclude scalp, palms, and soles from the assessment/scoring.

Percent BSA with Atopic Dermatitis: The number of handprints of skin afflicted with atopic dermatitis in a body region can be used to determine the extent (%) to which a body region is involved with atopic dermatitis (Table 5). When measuring, the handprint unit refers to the size of each individual subject’s hand with fingers in a closed position.

090177e18dabc776\0.1\Draft\Versioned On:07-Feb-2018 10:11 (GMT)

Table 5. Handprint Determination of Body Region Surface Area (BSA)

Body Region	Total Number of Handprints in Body Region*	Surface Area of Body Region Equivalent of One Handprint*
Head and Neck	10	10%
Upper Limbs	20	5%
Trunk (including axillae and groin/genitals)	30	3.33%
Lower Limbs (including buttocks)	40	2.5%

Handprint refers to the hand size of each individual subject.

* The number of handprints will be for the entire body region; these values will not be adjusted for exclusion of scalp, palms, and soles from the BSA assessment.

The extent (%) to which each of the four body regions is involved with atopic dermatitis is categorized to a numerical Area Score using a non-linear scaling method according to the following BSA scoring criteria (Table 6).

Table 6. Eczema Area and Severity Index (EASI) Area Score Criteria

Percent BSA with Atopic Dermatitis in a Body Region	Area Score
0%	0
>0 - <10%	1
10 - <30%	2
30 - <50%	3
50 - <70%	4
70 - <90%	5
90 - 100%	6

Body Region Weighting: Each body region is weighted according to its approximate percentage of the whole body (Table 7).

Table 7. Eczema Area and Severity Index (EASI) Body Region Weighting

Body Region	Body Region Weighting
Head and Neck	0.1
Upper Limbs	0.2
Trunk (including axillae and groin/genitals)	0.3
Lower Limbs (including buttocks)	0.4

* No adjustment for body regions excluded for assessment

In each body region, the sum of the Clinical Signs Severity Scores for erythema, induration/papulation, excoriation, and lichenification is multiplied by the Area Score and by the Body Region Weighting to provide a body region value, which is then summed across all four body regions resulting in an EASI score as described in Equation 3.

$$\text{Equation 3: } EASI = 0.1Ah(Eh+Ih+Exh+Lh) + 0.2Au(Eu+Iu+ExU+Lu) + 0.3At(Et+It+Ext+Lt) + 0.4Al(El+Il+Exl+Ll)$$

A = Area Score; E = erythema; I = induration/papulation; Ex = excoriation; L = lichenification; h = head and neck; u = upper limbs; t = trunk; l = lower limbs

090177e18dabc776\0.1\Draft\Versioned On:07-Feb-2018 10:11 (GMT)

The EASI score can vary in increments of 0.1 and range from 0.0 to 72.0, with higher scores representing greater severity of atopic dermatitis.

Appendix 4. Body Surface Area (BSA)

BSA Efficacy will be derived from the sum of the BSA in handprints across 4 body regions assessed as part of the EASI assessment (Table 5). Handprint refers to that of each individual subject for their own measurement. The BSA Efficacy ranges from 0 to 100%, with higher values representing greater severity of atopic dermatitis. Since the scalp, palms, and soles will be excluded from the BSA (Efficacy) assessment, the maximum possible value will be less than 100%.

Appendix 5. Scoring Atopic Dermatitis (SCORAD)

SCORAD is a validated scoring index for atopic dermatitis, which combines extent (0-100), severity (0-18), and subjective symptoms (0-20) based on pruritus and sleep loss, each scored (0-10).

Extent (A, maximum of 100%)

To determine extent of AD, rule of 9 is used to calculate body surface area affected by AD as a percentage of the whole body surface area. Body surface area as percentage of total body surface area for each body region is as follows:

- *Head and neck 9%;*
- *Upper limbs 9% each;*
- *Lower limbs 18% each;*
- *Anterior trunk 18%;*
- *Back 18%;*
- *1% for genitals.*

The score for each body region is added up to determine the BSA affected by AD (A), which has a possible maximum of 100%.

Severity (B, maximum of 18)

A representative area of AD is selected. In this area, the severity of each of the following signs is assessed as none (0), mild (1), moderate (2) or severe (3).

- *Erythema (reddening);*
- *Edema (swelling);*

- *Oozing/crusting*;
- *Excoriation (scratch marks)*;
- *Skin thickening (lichenification)*;
- *Xerosis (dryness) (this is assessed in an area where there is no inflammation)*.

The severity scores are added together to give 'B' (maximum of 18).

Subjective Symptoms (C, maximum of 20)

Subjective symptom (ie. itch and sleeplessness) are each scored by the subject or caregiver using a numeric rating scale (NRS) where “0” is no itch (or no sleeplessness) and “10” is the worst imaginable itch (or sleeplessness). These scores are added to give “C” (maximum of 20).

The SCORAD for an individual is calculated by the formula: $A/5 + 7B/2 + C$ (can range from 0 to 103).

Appendix 6. Pruritus Numeric Rating Scale (NRS)

Severity of Pruritus

The severity of itch (pruritus) due to atopic dermatitis will be assessed using a horizontal NRS (Appendix 6). Subjects will be asked to assess their “worst itching due to atopic dermatitis over the past 24 hours” on a NRS anchored by the terms “no itching” (0) and “worst possible itching” (10).

Frequency of Pruritus

The frequency of itch (pruritus) due to atopic dermatitis will be assessed using a horizontal NRS (Appendix 6). Subjects will be asked to assess “frequency of itching due to atopic dermatitis over the past 24 hours” on a NRS anchored by the terms “never/no itching” (0) and “always/constant itching” (10). The pruritus NRS should be completed as per Schedule of Activities.

Severity of Pruritus

Select the number that best describes your itching due to Atopic Dermatitis over the past 24 hours (check one number only).

										
0	1	2	3	4	5	6	7	8	9	10
No itching					Worst possible itching					

Frequency of Pruritus

Select the number that best describes frequency of itching due to Atopic Dermatitis over the past 24 hours (check one number only).

										
0	1	2	3	4	5	6	7	8	9	10
Never/No itching					Always/constant itching					

Appendix 7. Patient Global Assessment (PtGA)

The PtGA asks the subject to evaluate the overall cutaneous disease at that point in time on a single-item, 5-point scale (Appendix 5). The same category labels used in the Physician’s Global Assessment will be used for the Patient Global Assessment, ie, “severe (4)”, “moderate (3)”, “mild (2)”, “almost clear (1)”, and “clear (0)”. The PtGA should be completed as per Schedule of Activities.

Appendix 8. Dermatology Life Quality Index (DLQI)

The DLQI is a general dermatology questionnaire that consists of 10 items that assess subject health-related quality of life (daily activities, personal relationships, symptoms and feelings, leisure, work and school, and treatment) (Appendix 7). It has been extensively used in clinical trials for AD. The DLQI is a psychometrically valid and reliable instrument that has been translated into several languages, and the DLQI total scores have been shown to be responsive to change. The minimally important difference for the DLQI has been estimated as a 2 to 5 point change from baseline. The DLQI should be completed as per Schedule of Activities.

090177e18dabc776\0.1\Draft\Versioned On:07-Feb-2018 10:11 (GMT)

1.	Over the last week, how itchy, sore, painful or stinging has your skin been?	Very much A lot A little Not at all	   	
2.	Over the last week, how embarrassed or self conscious have you been because of your skin?	Very much A lot A little Not at all	   	
3.	Over the last week, how much has your skin interfered with you going shopping or looking after your home or garden?	Very much A lot A little Not at all	   	Not relevant 
4.	Over the last week, how much has your skin influenced the clothes you wear?	Very much A lot A little Not at all	   	Not relevant 
5.	Over the last week, how much has your skin affected any social or leisure activities?	Very much A lot A little Not at all	   	Not relevant 
6.	Over the last week, how much has your skin made it difficult for you to do any sport?	Very much A lot A little Not at all	   	Not relevant 
7.	Over the last week, has your skin prevented you from working or studying?	yes no	 	Not relevant 
	If "No", over the last week how much has your skin been a problem at work or studying?	A lot A little Not at all	  	
8.	Over the last week, how much has your skin created problems with your partner or any of your close friends or relatives?	Very much A lot A little Not at all	   	Not relevant 
9.	Over the last week, how much has your skin caused any sexual difficulties?	Very much A lot A little Not at all	   	Not relevant 
10.	Over the last week, how much of a problem has the treatment for your skin been, for example by making your home messy, or by taking up time?	Very much A lot A little Not at all	   	Not relevant 

Appendix 9. Patient-Oriented Eczema Measure (POEM)

The POEM is a 7-item PRO measure used to assess the impact of AD over the past week (Appendix 8). The POEM should be completed as per Schedule of Activities.

090177e18dabc776\0.1\Draft\Versioned On:07-Feb-2018 10:11 (GMT)

Please circle one response for each of the seven questions below about your eczema.
Please leave blank any questions you feel unable to answer.

1. Over the last week, on how many days has your skin been itchy because of your eczema?

No days 1-2 days 3-4 days 5-6 days Every day

2. Over the last week, on how many nights has your sleep been disturbed because of your eczema?

No days 1-2 days 3-4 days 5-6 days Every day

3. Over the last week, on how many days has your skin been bleeding because of your eczema?

No days 1-2 days 3-4 days 5-6 days Every day

4. Over the last week, on how many days has your skin been weeping or oozing clear fluid because of your eczema?

No days 1-2 days 3-4 days 5-6 days Every day

5. Over the last week, on how many days has your skin been cracked because of your eczema?

No days 1-2 days 3-4 days 5-6 days Every day

6. Over the last week, on how many days has your skin been flaking off because of your eczema?

No days 1-2 days 3-4 days 5-6 days Every day

7. Over the last week, on how many days has your skin felt dry or rough because of your eczema?

No days 1-2 days 3-4 days 5-6 days Every day

Appendix 10. Hospital and Anxiety Depression Scale (HADS)

The HADS is a 14-item PRO measure used to detect states of anxiety and depression over the past week (Appendix 9). The HADS should be completed as per Schedule of Activities.

090177e18dabc776\0.1\Draft\Versioned On:07-Feb-2018 10:11 (GMT)

1. I feel tense or 'wound up'
 
 3 Most of the time
 
 2 A lot of the time
 
 1 From time to time, occasionally
 
 0 Not at all
 
2. I still enjoy the things I used to enjoy
 
 0 Definitely as much
 
 1 Not quite so much
 
 2 Only a little
 
 3 Hardly at all
 
3. I get a sort of frightened feeling as if something awful is about to happen
 
 3 Very definitely and quite badly
 
 2 Yes but not too badly
 
 1 A little, but it doesn't worry me
 
 0 Not at all
 
4. I can laugh and see the funny side of things
 
 0 As much as I always could
 
 1 Not quite so much now
 
 2 Definitely not so much now
 
 3 Not at all
	
5. Worrying thoughts go through my mind
 
 3 A great deal of the time
 
 2 A lot of the time
 
 1 Not too often
 
 0 Very little
 
6. I feel cheerful
 
 3 Never
 
 2 Not often
 
 1 Sometimes
 
 0 Most of the time
 
7. I can sit at ease and feel relaxed
 
 0 Definitely
 
 1 Usually
 
 2 Not often
 
 3 Not at all
 
8. I feel as if I am slowed down
 
 3 Nearly all of the time
 
 2 Very often
 
 1 Sometimes
 
 0 Not at all

--	--


9. I get a sort of frightened feeling like 'butterflies' in the stomach
 
 0 Not at all
 
 1 Occasionally
 
 2 Quite often
 
 3 Very often
 
10. I have lost interest in my appearance
 
 3 Definitely
 
 2 I don't take as much care as I should
 
 1 I may not take quite as much care
 
 0 I take just as much care as ever
 
11. I feel restless as if I have to be on the move
 
 3 Very much indeed
 
 2 Quite a lot
 
 1 Not very much
 
 0 Not at all
	
12. I look forward with enjoyment to things
 
 0 As much as I ever did
 
 1 Rather less than I used to
 
 2 Definitely less than I used to
 
 3 Hardly at all
 
13. I get sudden feelings of panic
 
 3 Very often indeed
 
 2 Quite often
 
 1 Not very often
 
 0 Not at all
 
14. I can enjoy a good book or radio or television program
 
 0 Often
 
 1 Sometimes
 
 2 Not often
 
 3 Very seldom

---	---

090177e18dabc776\0.1\Draft\Versioned On:07-Feb-2018 10:11 (GMT)

Appendix 11. Example SAS Code for Generalized Linear Mixed model for IGA

This code has been included as an example of generalized linear mixed model in SAS. The actual code may be adjusted, depending on the testing of programming and the data. No SAP amendment is needed if the actual code is different from the example code in this section. The common procedure of PROC GLIMMIX has been used. As our decision criteria are based on differences in proportions this procedure allows us to back transform and express the data in this format. The following code was written assuming the format of the input dataset is of the form:

DOSE	id	week	IGA Response
0	1	4	0
10	2	6	0
30	3	8	0
100	4	12	1

.....

```
/* SAS example code */
*** Model: GLIMMIX MODEL ***;
```

```
/* random trend logistic regression via GLIMMIX */
PROC GLIMMIX DATA=one METHOD= RSPLNOCLPRINT;
CLASS id week;
MODEL IGA = dose week dose*week / SOLUTION DIST=BINARY LINK=LOGIT;
RANDOM INTERCEPT / SUBJECT=id TYPE=UN GCORR SOLUTION;
RUN;
```

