8.1.1.1. Primary Analysis

The primary analysis is the analysis of the primary endpoint, IGA clear (0) or almost clear (1) and ≥ 2 points improvements at Week 12, based on the FAS population. NR approach will be used to handle missing values as described in [Section 7.1](#).

IGA response at Week 12 will be analyzed using the Emax dose-response model. The estimation of E_0 , E_{max} and ED_{50} will be reported in mean, standard deviation and 95% CI. These can be implemented by using PROC NL MIXED in SAS.

The three parameter Emax model is a non-linear equation such that the expected response E with or without baseline disease severity in the model can be written as:

$$E = E_0 + \frac{E_{max} Dose}{ED_{50} + Dose}$$

Where:

E is the logit function for the log odds of response $Logit(p)$.

E_0 is in placebo IGA response.

E_{max} is the difference between maximum achievable response (at infinite dose) and baseline.

ED_{50} is the dose that produces half maximal effect ($E_0 + E_{max}/2$).

The 3-parameter Emax model describes a dose response that starts at E_0 and smoothly increases to an asymptote. The fitted curve will be graphically displayed with 95% confidence band. Model based estimation of treatment effect for each dose compared to placebo will be presented with 95% confidence interval.

Sensitivity analyses for IGA will be performed with generalized linear mixed models (GLMM) on FAS population with OC. Fixed factors include treatment, covariates (baseline disease severity such as EASI score), visit and treatment by visit interaction. Random effect includes random intercept for each subject. These can be implemented with SAS PROC GLIMMIX. P-values and inference for odds ratios between treatments will be provided based on the link function of logit. A delta method will be used to obtain 90% confidence intervals

for the risk differences. The overall p-value for treatment effect at each time point may be also presented. In addition, logistic regression analysis including treatment, covariates (baseline disease severity) at each time point will be performed on FAS with NR missing value imputation.

When an Emax model does not adequately capture the dose-response relationship or the Emax model does not converge, analysis from GLMM on FAS with OC and/or logistic regression on FAS with NR imputation may be considered for decision making to characterize the dose-response with dose being considered as a continuous variable.

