8.1.1.2. Other Analysis of Binary Data

The analyses for other binary endpoints will be performed using GLMM on the FAS population with OC as described in [Section 8.1.1.1](#). Logistic regression analysis may be performed on FAS with NR imputation in case of convergence issues from GLMM.

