8.2.2.1. Analysis for the Primary Endpoint

The primary efficacy endpoint is the IGA response at Week 12. The primary analysis data will be based on FAS population with NR as missing value imputation method. Baseline is defined as the score for each assessment prior to the first dosing. .

The objective for the analysis of primary endpoint is to characterize the dose response in inducing clinical IGA reduction in subjects with moderate to severe atopic dermatitis. To achieve this objective, a three parameter Emax dose response model specified in [Section 8.1.1.1](#) will be used as the primary analysis approach to characterize the dose response relationship.

As sensitivity analyses, GLMM will be employed on IGA response from all visits including follow-up. These analyses will be carried out on the FAS population with OC as described in [Section 8.1.1.1](#). P-values and 90% confidence intervals for odds ratios between treatments and placebo will be computed at each visit. Logistic regression will be performed at each visit on FAS with NR as additional sensitivity analysis.

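### The SAP's only GLMM code fits dose as a straight line in mg, contradicting the treatment-factor model in the text; the continuous-dose fallback also conflicts with the pairwise Hochberg fallback

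*SAP*

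**What the plan says.** SAP 8.1.1.1 describes the sensitivity GLMM for IGA response in words: "Fixed factors include treatment, covariates (baseline disease severity such as EASI score), visit and treatment by visit interaction", with a random intercept per subject. SAP 8.2.2.1 states the output wanted from it: "P-values and 90% confidence intervals for odds ratios between treatments and placebo will be computed at each visit". SAP 8.1.1.2 extends the method: "The analyses for other binary endpoints will be performed using GLMM on the FAS population with OC", referring back to 8.1.1.1. The table in 8.2.5 lists GLMM as the primary approach for EASI50/75/90, pruritus NRS, SCORAD and 2-point IGA responses, and as a sensitivity approach for IGA response itself.

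SAP Appendix 11 holds the only GLMM code. Its CLASS statement names subject id and week only, and its model statement is "MODEL IGA = dose week dose*week". It has no baseline term and no statement requesting dose-against-placebo contrasts. The appendix adds: "No SAP amendment is needed if the actual code is different from the example code in this section".

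Two places say what happens if the Emax model fails. SAP 8.1.1.1 allows GLMM and/or logistic regression to "characterize the dose-response with dose being considered as a continuous variable". SAP 4.2.1 and 4.2.2 instead point to pairwise comparisons, with the Hochberg procedure holding the family-wise error at one-sided 0.05.

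**The concern.** In GLIMMIX, a variable left out of CLASS is numeric. The printed model therefore has one dose slope per visit and cannot separate the four doses. If it were used for the odds ratios that 8.2.2.1 requires, a strong effect at 200 mg alone would carry 10 mg to the same p-value. The study's primary objective is to evaluate four dose levels against placebo, so the analysis has to be able to say which doses differ.

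The fallback has a related problem. If a continuous-dose model is chosen when Emax fails, it yields one slope test, whereas Hochberg needs four distinct dose comparisons. The SAP gives no order between the two routes.

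**Working it through.** The plan states no figure for the GLMM. The rates used below, 10% on placebo and 43% on an effective dose, are those of SAP 4.2.4. That section's 95% power is reproduced as 94.7% with 50 per arm and one-sided 0.0125 (pooled normal approximation); with 40 per arm it is 88.3%. Nothing below depends on the power figure, and both arm sizes are shown.

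**1. Algebra.** With numeric dose, let b be the dose coefficient and g(w) the dose-by-week coefficient at visit w. Then

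- log odds ratio of dose d against placebo = d × (b + g(w))
- its standard error = d × SE(b + g(w))
- Wald z = (b + g(w)) / SE(b + g(w))

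The dose cancels, so z and p are the same for 10, 30, 100 and 200 mg, whatever the data.

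**2. The SAP's own example counts.** Appendix 12 lists 5, 9, 11, 18 and 21 responders of 30 on 0, 10, 30, 100 and 200 mg.

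Linear in mg: slope 0.010745, SE 0.002485, z = 4.32, two-sided p = 0.000015 for every dose.

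Dose as a factor, for example at 10 mg: odds ratio = (9 × 25)/(21 × 5) = 2.14; log = 0.762; SE = √(1/9 + 1/21 + 1/5 + 1/25) = 0.631; z = 1.21.

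| Dose | OR, linear | p, linear | OR, factor | p, factor |
|---|---|---|---|---|
| 10 mg | 1.11 | 0.000015 | 2.14 | 0.23 |
| 30 mg | 1.38 | 0.000015 | 2.89 | 0.086 |
| 100 mg | 2.93 | 0.000015 | 7.50 | 0.0011 |
| 200 mg | 8.58 | 0.000015 | 11.67 | 0.0001 |

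The identity is exact for odds ratios. For delta-method risk differences the z values range from 4.6 to 5.6, so all four doses are still significant together.

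**3. Random-intercept check.** One simulated six-visit data set, 50 per arm, only 200 mg active, was fitted by maximum likelihood. The Week 12 log odds ratios were 0.22, 0.65, 2.17 and 4.35, in the ratio 1:3:10:20, each with z = 5.57.

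**4. How often 10 mg is carried along.** Assume 10% on placebo, 10, 30 and 100 mg and 43% on 200 mg, a single Week 12 analysis, one-sided 0.05, and 3,000 trials per row.

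| Per arm | 10 mg significant, linear | 10 mg significant, factor |
|---|---|---|
| 40 | 99.3% | 3.6% |
| 50 | 99.9% | 3.4% |

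Fitting the line to these true rates gives a slope of 0.0103 per mg, so the 10 mg odds ratio is exp(0.103) = 1.11, and the 10 mg response is 8.2% against a fitted 7.5% on placebo. With no effect at any dose the linear test rejects in 4.3% (40 per arm) and 5.8% (50 per arm), close to nominal. It is a sound trend test that is wrong for dose-specific claims.

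**5. The fallback.** On the logit scale Emax is E0 + Emax × d/(ED50 + d). As ED50 grows with Emax/ED50 held fixed, this tends to E0 + (Emax/ED50) × d. The straight line is thus a special case of Emax, with less freedom. Hochberg rejects every hypothesis when the largest p-value is at most alpha. Four equal p-values are therefore all rejected whenever the one slope p is at most 0.05, with no multiplicity penalty.

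**The case against.** The code is explicitly an example that may change without an amendment, and its comment calls it "random trend logistic regression via GLIMMIX". Numeric dose is legitimate in a trend model. The printed code requests no per-dose contrast, so it outputs no per-dose p-value as it stands. The text in 8.1.1.1 already requires treatment as a factor and the baseline covariate, and 8.1.1.2 sends the other binary endpoints to that text without citing Appendix 11. All of this stands.

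A reader might infer that every binary secondary endpoint will be analysed with dose linear in mg, or that the words "with dose being considered as a continuous variable" in 8.1.1.1 make the example code binding. The documents support neither. That sentence covers only Emax failure on IGA response, is permissive, and aims at describing dose response. It does not redefine the sensitivity or secondary-endpoint GLMM.

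It is also fair that the 99% figure rests on an effect at the top dose only and that an odds ratio of 1.1 would hardly look like a success. The figure shows that the p-value carries no information specific to 10 mg; it does not show that 10 mg would be judged effective.

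Finally, a simpler model is a defensible response to non-convergence, and a pairwise route already exists in 4.2.1 and 4.2.2. What remains is that the only GLMM code disagrees with the model and outputs the text demands, and that the two fallbacks are unreconciled.

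**Conclusion.** The contradiction is real and worth correcting. As printed, the Appendix 11 model cannot supply the separate dose-against-placebo odds ratios required by 8.2.2.1, and it omits the covariate named in 8.1.1.1. The equality of z and p across doses is exact on the log-odds scale and needs no assumption beyond the printed CLASS and model statements. The 99% rate does rest on assumptions: the SAP's design rates, an effect at 200 mg only, a single-visit logistic fit, and 40 or 50 per arm. The Appendix 12 counts are illustrative and are not trial data.

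Because the text governs, this is a text/code mismatch and not evidence of how the final analyses would be run. Exposure is greatest for the binary secondary endpoints, where GLMM is the primary approach; for IGA at Week 12 it is a sensitivity analysis.

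The fallback conflict lies in the body of the SAP, so the example label does not excuse it. Sections 8.1.1.1 and 4.2.1–4.2.2 name different routes for the same event, and the continuous-dose route cannot give Hochberg four distinct p-values.

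**What to change.** In Appendix 11, add dose to CLASS with placebo as reference, add baseline severity to the model, and add contrasts of each dose against placebo at each visit.

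In 8.1.1.1, state that when Emax fails or does not converge, the dose-against-placebo decision uses logistic regression or GLMM with dose as a five-level factor, and that its p-values feed the Hochberg procedure in 4.2.2. Keep any continuous-dose model as a separately labelled trend analysis with its own code, and say that it supports no claim about an individual dose.

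The cost is a few lines of example code and one or two SAP sentences, with no change to data collection or sample size.
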